	[REDACTED]	[REDACTED]

	
[REDACTED]
	
	
[REDACTED]
	
[REDACTED]

	
[REDACTED]
	
[REDACTED]

V4.0 27-NOV-2024	
[REDACTED]
	
[REDACTED]

TRIAL SYNOPSIS

Trial Title A prospective, single-centre, randomised, double-blind, placebo-controlled, phase I, First-In-Human (FIH) trial evaluating the safety and tolerability of single and multiple ascending oral doses of IRL757 in healthy volunteers.	
Trial code IRL757C001	EU trial no 2024-511426-31-00
Trial period Estimated date of first subject enrolled: Q2 2024 Estimated date of last subject completed: Q1 2025	Phase of development Phase I, FIH
Trial background IRL757 [REDACTED] is a novel small molecule compound developed for the treatment of apathy in neurodegenerative disorders. This is a FIH trial of IRL757 with the aim to study safety, tolerability and PK following single oral ascending doses and subsequent repeated dosing of the compound administered to healthy volunteers.	
Trial design and trial population Single Ascending Dose (SAD) part: A randomised, double-blind, placebo-controlled single ascending dose trial in healthy volunteers. Multiple Ascending Dose (MAD) part: A randomised, double-blind, placebo-controlled multiple dosing trial in healthy volunteers.	
Objectives Primary objective: To evaluate the safety and tolerability of IRL757 after single and repeated dosing in healthy volunteers. Secondary objectives: 
 1. To determine the single and multiple dose pharmacokinetic (PK) characteristics of IRL757 and its 3 main metabolites in healthy volunteers. 2. To evaluate the interaction with food after single oral dosing of IRL757 on its PK characteristics and its 3 main metabolites in healthy volunteers. Exploratory objective: To characterize the metabolite profile in human plasma and urine and compare metabolite exposures between human and the safety species rat and dog.	

Endpoints

Primary endpoints: Safety assessments

- Frequency, seriousness and intensity of Adverse Events (AEs)
- Physical examination
- Columbia-Suicide Severity Rating Scale (C-SSRS)
- Electrocardiogram (ECG) recordings
- Telemetry (SAD part of the trial only)
- Vital signs (blood pressure, heart rate and body temperature)
- Safety laboratory measurements

Secondary endpoints: PK assessments

- SAD part: Area under the plasma concentration-time curve $AUC_{0-\infty}$, AUC_t , AUC_{0-24h} , maximum concentration (C_{max}), time to maximum concentration (T_{max}), terminal elimination rate constant (λ_{dz}), terminal half-life ($T_{1/2}$), total apparent clearance of drug from plasma (CL/F), volume of distribution (V_z/F), amount excreted in urine (A_e), fraction of the dose excreted in urine (F_e) (for IRL757), renal clearance CL_R .
- Relative bioavailability after fed and fasting conditions determined from AUC_t and $AUC_{0-\infty}$, and C_{max} .
- MAD part, Day 1: $AUC_{0-\tau}$, C_{max} , T_{max} , λ_{dz} , $T_{1/2}$, Day 10: $AUC_{0-\tau}$, C_{max} , T_{max} , λ_{dz} , $T_{1/2}$, CL/F , V_z/F , fraction of the dose excreted in urine (F_e) (for IRL757) for the last dose interval in the morning of Day 10, renal clearance CL_R .
- Dose proportionality after single dose based on $AUC_{0-\infty}$ and C_{max} .
- Dose proportionality after multiple doses based on $AUC_{0-\tau}$ and C_{max} .
- Accumulation ratio (AR) after multiple doses based on C_{max} ratio and ratio $AUC_{0-\tau}$ (Day 10) to $AUC_{0-\tau}$ for the first dose interval on Day 1.

Exploratory endpoints

- Metabolite In Safety Testing (MIST) analysis of the metabolite profile in plasma in comparison with the metabolite profile in plasma from non-clinical safety studies.
- Profile of excreted metabolites in the urine.

Number of subjects planned

In the SAD part of the trial, forty (40) healthy subjects will be included (5 cohorts, 8 subjects in each cohort, randomised 3:1). Six (6) additional subjects will be included in a food interaction sub-study.

In the MAD part of the trial, up to 36 healthy subjects will be included in 2-3 cohorts with twelve (12) subjects in each cohort (up to 3 cohorts depending on the results of the SAD part of the trial, 12 subjects in each cohort, randomised 3:1).

If indicated by emerging data and recommended by the internal safety review committee (iSRC), 1 optional cohort (8 subjects) may be added to the SAD part of the trial, and 1 optional cohort (12 subjects) to the MAD part of the trial.

Diagnosis and main eligibility criteria

Healthy volunteers 18-55 years of age inclusive, with a weight of 50 to 110 kg, who are willing to comply with trial procedures and who have given written consent, will be considered eligible for participation in the trial. Female volunteers of childbearing potential must agree to use a highly effective method of contraception during the trial period to prevent pregnancy. Male volunteers must agree to use adequate contraception during the trial period to prevent pregnancy of a female partner.

Methodology

The **SAD part of the trial** will be a parallel group design with up to five (5) pre-defined ascending dose levels of IRL757 (see Table 1 below). Intermediary dose levels may be considered if recommended by the iSRC.

Forty (40) eligible and consenting subjects will be included in one (1) of five (5) cohorts, eight (8) subjects in each cohort. At each dose level, two (2) subjects will be given placebo, and six (6) subjects will be given IRL757.

Table 1 SAD Dosing cohorts/groups

Sequence No / Group		Cohort 1 (n=8)		Cohort 2 (n=8)		Cohort 3 (n=8)		Cohort 4 (n=8)		Cohort 5 (n=8)	
1	n=2	Placebo (1)	■ (1)	Placebo (1)	■ (1)	Placebo (1)	■ (1)	Placebo (1)	■ (1)	Placebo (1)	■ (1)
2	n=3	Placebo (1)	■ (5)	Placebo (1)	■ (5)	Placebo (1)	■ (5)	Placebo (1)	■ (5)	Placebo (1)	■ (5)
3	n=3										

* tentative dose that may change upon iSRC recommendation.

The eight (8) subjects in a cohort will be divided into at least three (3) groups with two (2) subjects in the first group and three (3) subjects in the following two (2) groups. In the first group at each dose level, a “sentinel group” of two (2) subjects (one [1] active drug/ one [1] placebo) will be dosed first and closely observed for 24 hours before proceeding to dose the remaining subjects, in two (2) groups with three (3) subjects in each with an interval of at least 30 minutes between subjects. The subsequent groups will be dosed approximately 24 hours apart.

There will be an interval of at least one (1) week between each dose level to allow time for PK and safety data to be analysed, evaluated and reviewed by the iSRC. The iSRC will have the choice to recommend to escalate the dose as planned, reduce or increase the dose escalation step, repeat the dose, reduce the dose or terminate the trial. Should dose adjustments be recommended the adjusted dose increments will remain in a somewhat similar design as in Table 1.

Screening (Visit 1) will take place between Day -28 and Day -1.

Eligible subjects will be confined to the research clinic from the evening before each dosing (Day -1) until 48 hours post-dose (Day 3). The subjects should be fasting overnight (10 hours) before dose administration on Day 1. During the in-clinic period, PK blood sampling and urine sampling will be performed, from IMP administration until 48 hours post-dose and until 24 hours post-dose respectively.

A Follow-up Visit will be performed 5-10 days after administration of Investigational Medicinal Product (IMP).

The food interaction sub-study will include six (6) additional subjects. The six subjects will be administered IRL757 in fasted and fed conditions. A standardized breakfast meal will be consumed within 30 minutes prior to IMP administration, in order to study potential food interactions. After the completion of cohort 4, safety and PK data will be evaluated to determine which dose level will be used for the food interaction sub-study. For each administration, the subjects will be confined to the research clinic from the evening before dosing (Day -1) until at least 48 hours after administration (Day 3).

In the MAD part of the trial, 24 or 36 eligible and consenting subjects will be allocated to one of two (2) or three (3) cohorts; IRL757 Dose Level 1, IRL757 Dose Level 2, and IRL757 Dose Level 3 if applicable, with 12 subjects in each cohort. Within each cohort subjects will be randomly assigned to treatment with placebo or IRL757; three (3) subjects will be given placebo, and nine (9) subjects will be given IRL757.

The 12 subjects in a cohort will be divided into four (4) groups; a sentinel group, two (2) groups of three (3) subjects each and one (1) group of four (4) subjects. In each cohort, the “sentinel group” of two (2) subjects (one [1] active drug/ one [1] placebo) will be dosed first and closely observed for 24 hours before starting the dosing in the following group. Subsequent groups in the cohort will be dosed approximately 24 hours apart. In each group the subjects will be dosed with an interval of at least 30 minutes between subjects. It is foreseen that subjects will be treated with two (2) daily oral doses of IRL757 or placebo administered at the same time during ten (10) consecutive days (the dosing interval is subject to change and will be confirmed depending on the results from the SAD part of the trial).

There will be an interval of at least one (1) week between last administration in a cohort and initiation of next cohort to allow time for PK and safety data to be analysed, evaluated and reviewed by the iSRC. The iSRC will have the choice to recommend to escalate the dose as planned, reduce or increase the dose escalation step, repeat the dose, reduce the dose or terminate the trial.

The decision on dose levels will be done following the SAD part of the trial and a cautious selection of dose will be done if dosing is expected to approach the exposure limit.

Screening (Visit 1) will take place between Day -28 and Day -1.

Eligible subjects will be confined to the research clinic from the evening before first dosing (Day -1) until Day 11 and will come back to the clinic on Day 12 for extended PK and safety samples (including 48 hours post the last morning dose). The subjects should be fasting overnight (10 hours) before dose administration on Day 1 and Day 10. A Follow-up Visit will be performed 5-10 days after last administration of IMP.

An additional third cohort (IRL757 Dose Level 3), with twelve (12) additional subjects may be implemented following the review of data of the SAD part of the trial. The cohorts are described in Table 2.

Table 2 MAD dosing groups

Cohort	Dose	Groups	
Cohort 1 (n=12)	Dose Level 1	2 + 3 + 3 + 4	Sentinel group (n=2): 1 active, 1 placebo Subsequent groups (n=3+3+4): 8 active, 2 placebo
Cohort 2 (n=12)	Dose Level 2	2 + 3 + 3 + 4	
Cohort 3 (n=12)	Dose Level 3	2 + 3 + 3 + 4	

Investigational Medicinal Products (IMP), dosage and mode of administration

IRL757 half-life is expected to be 2-7 hours.

IRL757 capsules [REDACTED]

Placebo capsules: [REDACTED]

Duration of treatment

Subjects included in the SAD part will be treated with one (1) single oral dose of IRL757 or placebo (see Table 1).

Subjects included in the food interaction sub-study will be treated with two (2) oral doses of IRL757.

Subjects included in the MAD part will receive two (2) daily oral doses of IRL757 or placebo for ten (10) consecutive days. The number of daily doses in the MAD part of the trial will be confirmed following review of PK data from the SAD part of the trial.

Duration of each subject's involvement in the trial

Subjects will be screened for eligibility according to trial-specific inclusion/exclusion criteria at Visit 1 (Screening visit) within four (4) weeks prior to start of IMP administration.

A Follow-up Visit will be performed for all subjects 5-10 days after last administration of IMP.

In the food interaction sub-study, each subject's involvement duration will also depend on how soon the second dose will be given after the first IMP administration (may vary between 5 half-lives and 14 days).

Total duration of involvement per subject:

- SAD part of the trial: from 7 days up to 39 days
- food interaction sub-study: up to 54 days
- MAD part of the trial: from 16 days up to 48 days

Statistical methods

No formal sample size calculation has been performed for this trial. The size of the cohorts/dose groups is considered sufficient to provide adequate information on the safety and PK parameters for the purpose of this trial.

All statistical calculations will be performed using the SAS® version 9.4 or later program (SAS Institute Inc., Cary, NC, USA). The statistical analyses will only include descriptive statistics reflecting the explorative nature of the trial. In general, the data will be presented by treatment and dose group. The data for subjects receiving placebo will be presented pooled across groups.

Continuous data will be summarised by treatment and dose group using number of observations, mean, standard deviation (SD), median, minimum and maximum. Categorical data will be summarised by treatment and dose group using the number and percentage of subjects in each category.

Unless otherwise stated, statistical evaluations will be based on all subjects who have received randomised treatment with IMP and have available data. Evaluations will be done according to actual treatment regardless of randomisation. A dose group will consist of all subjects treated with that dose

regardless of dose panel. Similarly, the placebo group will consist of all subjects treated with placebo regardless of dose panel. The Full Analysis Set (FAS) data set will be used for the safety and tolerability assessments.

The Per Protocol Analysis Set (PPAS) comprises data from all subjects randomised and treated with evaluable PK parameter data, and no major protocol deviations with an impact on PK data. The PPAS set will be used for presentation of PK endpoints.

The PK parameters will be calculated by non-compartmental analysis (NCA) using the software Phoenix WinNonlin® version 8.3 or later (Certara, USA).

Table 3 Schedule of events, SAD part of the trial (fasted condition)

Visit	Visit 1	Visit 2				Follow-up Visit
Day	Screening	In-clinic				Ambulatory
	-28 to -1	-1	1	2	3	5-10 days after IMP administration
Informed consent	X					
Demographics and medical/surgical history	X					
Inclusion/exclusion criteria	X		X ¹			
Physical examination	X		X ¹		X ²	X
C-SSRS	X				X	X
Weight, BMI	X	X				X
Height	X					
Pregnancy test ¹⁰	X	X				X
Blood pressure, heart rate, respiratory rate	X	X	X ³	X ³	X	X
Body temperature		X		X	X	
Haematology, clinical chemistry, coagulation	X	X			X	X
HIV, Hepatitis B and C	X					
Drugs of abuse	X	X				
Alcohol screen	X	X				
ECG	X	X ⁶	X ⁴	X ⁴	X ⁴	X
Telemetry ⁵			X	X		
Randomisation			X ¹			
IMP administration			X			
Blood sampling (PK and MIST analysis)			X ⁷	X ⁸	X ⁸	
PK urine sampling ⁹			X	X		
Baseline symptoms	X	X				
AE reporting			X	X	X	X
Concomitant medications	X	X	X	X	X	X
Admission to clinic		X				

¹ Pre-dose.

² Symptom-driven physical examination

³ Pre-dose and 30 min, 1, 2, 4, 8, 12 and 24 hours post-dose.

⁴ Pre-dose, 1, 2, 3, 6, 12, 24 and 48 hours post-dose.

⁵ Cardiac surveillance up to 24 hours post-dose.

⁶ Triplicate ECGs separated by at least 1 min.

⁷ Within 60 min pre-dose and 20 (±2) min, 40 (±4) min, 1 hour (±6 min), 2 hours (±12 min), 3 hours (±18 min), 4 hours (±24 min), 6 hours (±30 min), 8 hours (±30 min), 10 hours (±30 min), and 12 hours (±30 min) post-dose. The sample for MIST analysis is only applicable from dose level 2 and onwards.

⁸ 24 hours (±1 hour) post-dose and 48 hours (±1 hour) post-dose. The sample for MIST analysis is only applicable from dose level 2 and onwards.

⁹ Urine collection in fractions 0-6, 6-12 and 12-24 h post-dose. For SAD cohort 5 also 24-48 h post-dose. Subjects to empty their bladder prior to dose for urine collection (a pre-dose sample will be retained). A sample (approx. 2mL) from each fraction will also be kept for metabolite pattern analysis from dose level 2 and onwards.

¹⁰ Serum at screening, urine at Day -1 and Follow-up.

Table 4 Detailed schedule of events, SAD part of the trial, in-clinic Day -1 to Day 3 (fasted condition)

Visit No.	Visit 2															
Day	Day -1	Day 1													Day 2	Day 3
Time /assessment	Admission	Pre-dose	0	20min	30min	40min	1 h	2 h	3 h	4 h	6 h	8 h	10h	12 h	24 h	48 h
Inclusion/exclusion criteria		X														
Physical examination		X														X ¹
C-SSRS																X
Weight, BMI	X															
Pregnancy test	X ⁷															
Blood pressure, heart rate, respiratory rate	X	X			X		X	X		X		X		X	X	X
Body temperature	X														X	X
Haematology, clinical chemistry, coagulation	X															X
Drugs of abuse	X															
Alcohol screen	X															
ECG	X ²	X ³					X	X	X		X			X	X	X
Telemetry		X	X													
Randomisation		X														
IMP administration			X													
Blood sampling ^{4, 6} (PK and MIST analysis)		X		X		X	X	X	X	X	X	X	X	X	X	X
PK urine sampling ⁵		X	X													
Baseline symptoms	X	X														
AE reporting			X													X
Concomitant medications	X	X	X													X

¹ Symptom-driven physical examination.

² Triplicate ECGs separated by at least 1 min at Day -1.

³ Within 60 min prior to dose at Pre-dose.

⁴ Within 60 min pre-dose and 20 (±2) min, 40 (±4) min, 1 hour (±6 min), 2 hours (±12 min), 3 hours (±18 min), 4 hours (±24 min), 6 hours (±30 min), 8 hours (±30 min), 10 hours (±30 min), 12 hours (±30 min), 24 hours (±1 hour) and 48 hours (±1 hour) post-dose.

⁵ Urine collection in fractions 0-6, 6-12 and 12-24 h post-dose. For SAD cohort 5 also 24-48 h post-dose. Subjects to empty their bladder prior to dose for urine collection (a pre-dose sample will be retained). A

sample of approx. 2 mL from each fraction will also be kept and divided into two aliquots for metabolite pattern analysis from dose level 2 and onwards.

⁶ Plasma obtained at each time point will be divided into two samples, one for PK analysis and one for MIST analysis. Each of these samples will be separated into two aliquots. The sample for MIST analysis is only applicable from dose level 2 and onwards.

⁷ Urine test.

Table 5 Schedule of events, SAD part of the trial, food interaction sub-study

Visit	Visit 1	Visit 2				Visit 3 ¹				Follow-up Visit
Day	Screening	In-clinic				In-clinic				Ambulatory
	-28 to -1	-1	1	2	3	-1 fed	1 fed	2 fed	3 fed	5-10 days after last dose
Informed consent	X									
Demographics and medical/surgical history	X									
Inclusion/exclusion criteria	X		X ²							
Physical examination	X		X ²		X ³		X ³		X ³	X
C-SSRS	X				X				X	X
Weight, BMI	X	X				X				X
Height	X									
Pregnancy test ¹⁰	X	X				X				X
Blood pressure, heart rate, respiratory rate	X	X	X ⁴	X ⁴	X	X	X ⁴	X ⁴	X	X
Body temperature		X		X	X	X		X	X	
Haematology, clinical chemistry, coagulation	X	X			X	X			X	X
HIV, Hepatitis B and C	X									
Drugs of abuse	X	X				X				
Alcohol screen	X	X				X				
ECG	X	X ¹¹	X	X	X	X ¹¹	X	X	X	X
Standardized breakfast meal ⁸							X			
IMP administration ⁹			X				X			
PK blood sampling			X ⁵	X ⁶	X ⁷		X ⁵	X ⁶	X ⁷	
Baseline symptoms	X	X								
AE reporting			X	X	X	X	X	X	X	X
Concomitant medications	X	X	X	X	X	X	X	X	X	X
Admission to clinic		X				X				

¹ Visit 3 is performed after a minimum of 5 half-lives of the IMP and no later than 14 days after the first IMP administration.

² Pre-dose.

³ Symptom-driven physical examination.

⁴ Pre-dose and 30 min, 1, 2, 4, 8, 12 and 24 hours post-dose.

⁵ Within 60 min pre-dose and 20 (±2) min, 40 (±4) min, 1 hour (±6 min), 2 hours (±12 min), 3 hours (±18 min), 4 hours (±24 min), 6 hours (±30 min), 8 hours (±30 min), 10 hours (±30 min), and 12 hours (±30 min) post-dose.

⁶ 24 hours (±1 hour) post-dose.

⁷ 48 hours (±1 hour) post-dose.

⁸ Standardized breakfast meal is provided to the subject within 30 min prior to IMP administration.

⁹ The dose used for the food interaction sub-study will be determined after completion of Cohort 4 (Dose Level 4) in the SAD part of the trial.

¹⁰ Serum at screening, urine at Day -1 and Follow-up.

¹¹ Triplicate ECGs separated by at least 1 min.

Table 6 Detailed schedule of events, SAD part of the trial, food interaction sub-study, in-clinic Day -1 to Day 3

	In-clinic															
Visit No.	Visit 2 (fasted condition)/Visit 3 (fed condition)															
Day	Day -1	Day 1													Day 2	Day 3
Time /assessment	Admission	Pre-dose	0	20min	30min	40min	1 h	2 h	3 h	4 h	6 h	8 h	10 h	12 h	24 h	48 h
Inclusion/exclusion criteria		X														
Physical examination		X ⁸														X ⁹
C-SSRS																X
Weight, BMI	X															
Blood pressure, heart rate, respiratory rate	X	X			X		X	X		X		X		X	X	X
Body temperature	X														X	X
Haematology, clinical chemistry, coagulation	X															X
Pregnancy test	X ⁷															
Drugs of abuse	X															
Alcohol screen	X															
ECG	X ¹	X ²					X	X	X		X			X	X	X
Standardized breakfast meal		X ³														
IMP administration			X													
PK blood sampling ⁴		X		X		X	X	X	X	X	X	X	X	X	X	X
Baseline symptoms	X ⁵	X ⁵														
AE reporting	X ⁶	X ⁶	X													
Concomitant medications	X	X	X													

¹ Triplicate ECGs separated by at least 1 min at Day -1.

² Within 60 min prior to dose at Pre-dose.

³ Meal to be started within 30 min prior to administration of IMP. Applicable only to Visit 3 (fed condition).

⁴ Within 60 min pre-dose and 20 (±2) min, 40 (±4) min, 1 hour (±6 min), 2 hours (±12 min), 3 hours (±18 min), 4 hours (±24 min), 6 hours (±30 min), 8 hours (±30 min), 10 hours (±30 min), 12 hours (±30 min), 24 hours (±1 hour) and 48 hours (±1 hour) post-dose.

⁵ Applicable only to Visit 2 (fasted condition).

⁶ Applicable only to Visit 3 (fed condition).

⁷ Urine test.

⁸ Full physical examination at Visit 2. Symptom-driven physical examination at Visit 3.

⁹ Symptom-driven physical examination.

Table 7 Schedule of events MAD part of the trial

	Screening	In-clinic								Ambulatory	Follow-up
Visit	Visit 1	Visit 2								Visit 3	Visit 4
Day	Day -28 to -1	-1	1	2, 3, 4	5, 6	7	8, 9	10	11	12	5-10 days after last dose
Informed consent	X										
Demographics and medical/surgical history	X										
Inclusion/exclusion criteria	X		X ¹								
Physical examination	X		X ¹	X ²		X ²		X ²			X ²
C-SSRS	X					X			X		X
Weight, BMI	X	X						X			X
Height	X										
Pregnancy test ¹⁶	X	X									X
Blood pressure, heart rate, respiratory rate	X	X	X	X ¹⁸	X ¹⁸	X ¹⁸	X ¹⁸	X ¹⁸	X	X	X
Body temperature		X	X ¹⁸			X ¹⁸		X ¹⁸		X	
Haematology, clinical chemistry, coagulation ³	X		X ⁴	X ⁵		X		X ⁴		X	X
HIV, Hepatitis B and C	X										
Drugs of abuse	X	X									
Alcohol screen	X	X									
ECG	X	X ⁶	X ⁶	X ⁷	X ⁷	X ⁷	X ⁷	X ⁷	X	X	X
Randomisation			X ¹								
IMP administration ⁸			X	X	X	X	X	X			
PK blood sampling ¹⁷			X ⁹	X ¹⁰	X ¹⁰	X ¹¹	X ¹³	X ⁹	X ¹²	X ¹²	
MIST blood sampling ^{14, 17}			X	X				X	X	X	
PK urine sampling			X ¹					X ¹⁵	X ¹⁵		
Baseline symptoms	X	X									
AE reporting			X	X	X	X	X	X	X	X	X
Concomitant medications	X	X	X	X	X	X	X	X	X	X	X

¹ Pre-dose.

² Symptom-driven physical examination.

³ Coagulation parameters at Screening, Day 1, Day 7, Day 10 and Follow-up only.

⁴ Pre-dose and Day 10 safety samples taken in fasted condition.

⁵ At Day 2 and 4 only.

⁶ Triplicate ECGs separated by at least 1 min on Day -1. Within 60 min prior to morning dose on Day 1 and at 1, 2, 3, 6 and 12 hours post dose.

⁷ 2-4 hours post morning dose on Day 2-10.

⁸ Twice daily. Only 1 dose on Day 10, in the morning.

⁹ Day 1 and Day 10, first dose of the day: pre-dose (within 10 min), 20 (± 2) min, 40 (± 4) min, 1 hour (± 6 min), 2 hours (± 12 min), 3 hours (± 18 min), 4 hours (± 24 min), 6 hours (± 30 min), 8 hours (± 30 min), 10 hours (± 30 min), 12 hours, and 14 hours (± 30 min). Timepoints for PK sample collection are subject to change according to results from the SAD part of the trial and dose regimen. 12-, 24- and 48-hour samples are taken within 10 min pre-dose.

¹⁰ Days 2, 3, 4, 5 and 6: pre-dose (within 10 min prior morning dose of the day).

¹¹ Day 7, first dose of the day: pre-dose (within 10 min prior morning dose), 20 (± 2) min, 40 (± 4) min, 1 (± 6 min), 2 (± 12 min), 4 hours (± 24 min) post-dose. Timepoints for PK sample collection are subject to change according to results from the SAD part of the trial and dose regimen.

¹² Day 11: 24 hours post last morning dose (on Day 10) and Day 12: 48 hours post last morning dose (on Day 10).

¹³ Days 8 and 9: pre-dose (within 10 min prior morning dose of the day).

¹⁴ Same samples/timepoints as for PK blood sampling at Day 1 and Day 10 (up to 48 hours) will be used for MIST analysis.

¹⁵ Urine collection 0-24h in fractions 0-8h, 8-12h and 12-24h from morning dose on Day 10. Time interval for the fractions can be revised according to dose regimen chosen. A sample from each fraction will also be kept for metabolite pattern analysis.

¹⁶ Serum at screening, urine at Day -1 and Follow-up.

¹⁷ Each plasma sample obtained will be separated into two aliquots.

¹⁸ Once daily, within 1 hour post morning dose.

Table 8 Detailed schedule of events, MAD part of the trial, in-clinic period (Day -1 – Day 7)

	In-clinic period																				
Visit No.	Visit 2																				
Day	Day -1	Day 1														Day 2	Day 3	Day 4	Day 5	Day 6	Day 7
Time /assessment	Admission	Pre-dose	0	20min	30min	40min	1 h	2 h	3 h	4 h	6 h	8 h	10 h	12 h	14 h	24 h	48 h				
Inclusion/exclusion criteria		X																			
Physical examination		X														X ¹	X ¹	X ¹		X ¹	
C-SSRS																				X	
Weight, BMI	X																				
Pregnancy test	X ¹¹																				
Blood pressure, heart rate, respiratory rate	X	X		X			X	X		X		X		X		X ¹²	X ¹²	X ¹²	X ¹²	X ¹²	
Body temperature	X	X																		X ¹²	
Haematology, clinical chemistry, coagulation ²		X ³														X		X		X	
Drugs of abuse	X																				
Alcohol screen	X																				
ECG	X ⁴	X ⁴					X	X	X		X			X		X ⁵	X ⁵	X ⁵	X ⁵	X ⁵	
Randomisation		X																			
IMP administration			X											X		X ⁶	X ⁶	X ⁶	X ⁶	X ⁶	
PK blood sampling ⁷		X ⁸		X		X	X	X	X	X	X	X	X	X	X	X ¹⁰	X ¹⁰	X ¹⁰	X ¹⁰	X ⁹	
MIST blood sampling		X ⁸		X		X	X	X	X	X	X	X	X	X	X	X	X				
PK urine sampling		X																			
Baseline symptoms	X	X																			
AE reporting			X																		
Concomitant medications	X																				

¹ Symptom driven physical examination.

² Coagulation parameters at Day 1 and Day 7 only.

³ In fasted condition.

⁴ Triplicate ECGs separated by at least 1 min on Day -1. Within 60 min prior to morning dose on Day 1.

⁵ 2-4 hours post morning dose on Day 2-7.

⁶ Twice daily.

⁷ PK blood sampling timepoints are subject to change, depending on results from the SAD part of the trial and dose regimen.

⁸ Within 60 min prior to IMP administration.

⁹ First dose of the day: pre-dose (within 10 min prior IMP administration), 20 min, 40 min, 1, 2, 4 hours post-dose. Timepoints for PK sample collection are subject to change according to results from the SAD part of the trial and dose regimen.

¹⁰ First dose of the day: pre-dose (within 10 min prior IMP administration) for trough plasma concentration.

¹¹ Urine test.

¹² Once daily, within 1 hour post-morning dose.

Table 9 Detailed schedule of events, MAD part of the trial, in-clinic period (Day 8 - 11)

	In-clinic period															Ambulatory	
Visit No.	Visit 2															Visit 3	
Day	Day 8	Day 9	Day 10													Day 11	Day 12
Time /assessment			Pre-dose	0	20min	40min	1 h	2 h	3 h	4 h	6 h	8 h	10 h	12 h	14 h		
Physical examination			X ¹														
C-SSRS																X	
Weight, BMI			X ¹														
Blood pressure, heart rate, respiratory rate	X ¹⁰	X ¹⁰					X									X	X
Body temperature							X										X
Haematology, clinical chemistry, coagulation ³			X ²														X
ECG ⁴	X	X						X								X	X
IMP administration	X ⁵	X ⁵		X													
PK blood sampling ⁶	X ⁷	X ⁷	X ⁷		X	X	X	X	X	X	X	X	X	X	X	X ⁸	X ⁸
MIST blood sampling			X ⁷		X	X	X	X	X	X	X	X	X	X	X	X	X
PK urine sampling ⁹				X													
AE reporting	X	X	X													X	X
Concomitant medications	X	X	X													X	X

¹ Performed at any time during Day 10.

² In fasted condition.

³ Coagulation parameters at Day 10 only.

⁴ ECG 2-4 hours post morning dose on Day 8-10 (time confirmed based on the results from the SAD part of the trial).

⁵ Twice daily. Only 1 morning dose on Day 10.

⁶ PK blood sampling timepoints are subject to change, depending on results from the SAD part of the trial.

⁷ First dose of the day: pre-dose (within 10 min prior IMP administration) for trough plasma concentrations.

⁸ 24-hour PK sample after last morning dose and 48-hour PK sample after last morning dose.

⁹ Urine collection 0-24h in fractions 0-8h, 8-12h and 12-24h from morning dose on Day 10. Time interval for the fractions can be revised according to dose regimen chosen. A sample of approx. 2 mL from each fraction will also be kept for metabolite pattern analysis.

¹⁰ Once daily after Day 1, within 1 hour post-morning dose.

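### SAD part and food sub-study: no body temperature is scheduled between Day -1 and 24 h post-dose, so a transient temperature effect around peak exposure would be missed

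*Protocol*

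**What the plan says.** **Endpoint.** The protocol synopsis lists "Vital signs (blood pressure, heart rate and body temperature" among the primary safety endpoints. SAP 9.1.6 summarises body temperature with the other vital signs by part, treatment and dose group.

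**SAD schedule.** The Table 3 row reads "Body temperature X X X", with the marks under Day -1, Day 2 and Day 3. Table 4 places them at admission, 24 h and 48 h, and every column from pre-dose to 12 h is blank.

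**Food sub-study.** The Table 5 row reads "Body temperature X X X X X X": Days -1, 2 and 3 of the fasted period and the same days of the fed period. Table 6 agrees.

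**Other vital signs.** Footnote 3 of Table 3 and footnote 4 of Table 5 time blood pressure, heart rate and respiratory rate at "Pre-dose and 30 min, 1, 2, 4, 8, 12 and 24 hours post-dose".

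**Exposure and confinement.** The synopsis states that "IRL757 half-life is expected to be 2-7 hours". For the SAD part it also states: "Eligible subjects will be confined to the research clinic from the evening before each dosing (Day -1) until 48 hours post-dose (Day 3".

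**Baseline.** SAP 5.4 takes the last value before IMP exposure in each treatment period.

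**MAD schedule.** Table 7 attaches footnote 18, "Once daily, within 1 hour post morning dose", to temperature on Days 1, 7 and 10. Table 8 marks the Day 1 temperature at pre-dose.

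**The concern.** Vital signs in a first-in-human dose escalation should be observed while the drug is present at meaningful concentrations. For blood pressure, heart rate and respiratory rate the plan does this. For temperature, a component of the same endpoint, it schedules nothing from the evening before dosing until a full day after. If IRL757 briefly raised or lowered temperature around peak concentration, the scheduled data would show nothing at any SAD dose level. The safety review committee would then take its escalation decisions without planned temperature data from that window.

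There is a second, smaller weakness. With no Day 1 pre-dose reading, baseline falls back to the Day -1 value taken around evening admission. The 24 h and 48 h readings follow the clock time of a dose given after an overnight fast. A change from baseline within one group can then contain an evening-to-morning difference unrelated to treatment.

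**Working it through.** The documents give no sample size, power or other calculated figure on this point, so there is none to reproduce. The check has four steps.

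**1. Count scheduled readings between Day -1 admission and 24 h (Tables 3 to 6)**

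| Setting | Temperature | Blood pressure, heart rate, respiratory rate |
|---|---|---|
| SAD cohorts | 0 | 7 (pre-dose, 30 min, 1, 2, 4, 8, 12 h) |
| Food sub-study, fasted | 0 | 7 |
| Food sub-study, fed | 0 | 7 |

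The overview and detailed tables agree, so the blank is not a slip in one table.

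**2. Drug remaining at the first post-dose temperature**

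Input: half-life t of 2 to 7 h (protocol synopsis). Assumption: first-order elimination. Fraction remaining at 24 h = 2^(-24/t).

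- t = 2 h: 24/2 = 12 half-lives; 2^(-12) = 0.00024, or 0.02%.
- t = 4 h: 24/4 = 6 half-lives; 2^(-6) = 0.0156, or 1.6%.
- t = 7 h: 24/7 = 3.4 half-lives; 2^(-24/7) = 0.093, or 9.3%.

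At 48 h the largest value is 2^(-48/7) = 0.0086, below 0.9%.

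**3. Sensitivity to oral absorption**

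The documents give no absorption rate constant. I assumed ka from 0.5 to 4 per hour in a one-compartment model: C(t) proportional to [ka/(ka - k)] × [exp(-kt) - exp(-ka t)], with k = ln 2 / half-life.

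| Half-life | Tmax | C(24 h)/Cmax | AUC already elapsed at 24 h |
|---|---|---|---|
| 2 h | 0.7 to 2.4 h | 0.03% to 0.18% | over 99.9% |
| 7 h | 0.9 to 4.0 h | 10% to 17% | 88% to 90% |

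Across these assumptions the modelled peak falls between 0.7 and 4 h, inside the unobserved window. What remains at 24 h depends strongly on where in the 2 to 7 h range the true half-life lies.

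**4. Which comparisons the baseline affects**

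Under SAP 5.4 the SAD temperature baseline is the Day -1 value. The dosing hour is not stated. Morning is my inference from the 10-hour overnight fast and, in the fed period, the breakfast before dosing.

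- *Within-group change:* evening baseline against a presumably morning reading, so time of day may be mixed in.
- *Active against placebo (main SAD cohorts):* both arms follow one schedule, so the shift is expected in both and should largely cancel.
- *Fed against fasted (food sub-study, no placebo):* both periods use the same clock pattern, so the shift is again shared.

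**The case against.** The strongest reply is that the effect of the gap is easily overstated. Much of that reply stands.

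- A reader might infer that no drug effect on temperature could be seen. The figures do not support that. At a 7 h half-life about 9% of the drug remains at 24 h, or 10% to 17% of Cmax under the assumed absorption. The three main metabolites have no stated half-life, and an effect may outlast the concentration that caused it.
- A reader might infer that the evening baseline biases the comparison with placebo. It does not by itself, because placebo subjects share the schedule.
- A reader might infer that the SAD temperature table would be presented as reassuring. Nothing in the documents says so. The analysis is descriptive, and the SAD vital-sign table shells are not in the available text. A change-from-baseline layout is visible only in the MAD shell, Table VS 1.
- A reader might infer that the whole trial lacks temperatures on exposure. The MAD part takes them, with placebo control, within about 1 h after the morning dose on Days 7 and 10.
- Subjects are confined for 48 h, sentinels are closely observed for 24 h, AEs are recorded from dosing, and the main SAD cohorts have telemetry to 24 h.
- No available text names temperature as an expected risk. Only the protocol synopsis and schedules could be read, so a rationale may exist elsewhere. SAP Table 1 names only blood pressure and pulse under vital signs, although SAP 9.1.6 and the protocol endpoint list include temperature.

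These points narrow the concern without removing it. Observation, telemetry and AE reports are not scheduled temperature data, and MAD readings on Days 7 and 10 do not describe single doses across the SAD range. Agreement among the four tables suggests a deliberate choice, but the available text gives no reason for treating one component of the endpoint differently.

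**Conclusion.** The concern holds in a limited form. Followed as written, the plan yields no scheduled body temperature between Day -1 and 24 h at any of the five planned SAD dose levels or in either food period. A transient, concentration-linked effect that resolves before 24 h would be missed by the scheduled readings. A longer-lasting or metabolite-driven effect might still appear at 24 h or 48 h.

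The count of readings is certain from the tables. The size (3.4 to 12 half-lives; 9.3% to 0.02% remaining) rests on the protocol's expected half-life and first-order elimination. The time-of-day point rests on morning dosing and is confined to within-group change from baseline.

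The MAD discrepancy is separate. Under Table 7 there is no Day 1 pre-dose temperature and baseline reverts to Day -1; under Table 8 the first post-dose temperature is on Day 7. Footnote 10 of Table 9 does not settle it, because it is attached to the other vital signs.

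**What to change.** 1. In Tables 3 to 6, add body temperature at Day 1 pre-dose and at some of the existing post-dose vital-sign times within 12 h, for example 2, 4 and 8 h. The pre-dose value then becomes the SAP 5.4 baseline with no change to the SAP.
2. For cohorts already dosed, state in the report that SAD temperature was not scheduled between Day -1 and 24 h and supports no conclusion about effects near peak exposure. This may well apply: the protocol is version 4.0 of 27 November 2024, and first enrolment was estimated for Q2 2024.
3. Reconcile Table 7 (footnote 18) with Table 8 on the MAD Day 1 temperature time.

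**Cost.** With the example times, four readings per subject per dosing day, at times when staff already take vital signs. If no cohort had yet been dosed, that would be 40 × 4 = 160 readings in the main SAD cohorts and 6 × 2 × 4 = 48 in the food sub-study. It needs table and footnote edits, but no extra visit or sample.
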